#### **STUDY SUMMARY**

Title: Suturing with U-Technique versus Un-Reapproximated wound Edges during removal of Closed Thoracostomy-tube drain - A single centre Open-label randomized prospective trial (SUTURE TRIAL)

**Background:** Closed thoracostomy tube drainage or chest tube insertion is one of the most commonly performed procedures in thoracic surgery. There are several published evidence-based guidelines on safe performance of a chest tube insertion. However, there is absence of prospective controlled trials or systematic reviews indicating the safest technique of closing the wound created at the time of chest tube insertion and that best guarantees good wound and overall outcomes, post-chest tube removal. The use of a horizontal mattress non-absorbable suture or U- suture which is placed at the time of chest tube insertion and used to create a purse-string wound re-approximation at the time of tube removal has been an age-long and time-honored practice in most thoracic surgical settings. It has been established by a recent study that an occlusive adhesive-absorbent dressing can also be safely used to occlude the wound at the time of chest tube removal with good wound and overall outcomes though the study focused on tubes inserted during thoracic surgical operations.

Research Design: The study is an Open-label randomized prospective trial

**Methodology:** 142 consenting patients with indication for chest tube insertion, who meet the inclusion criteria for enrolment in the study will be randomly assigned into two balanced groups- Group A; that will have a Prolene 1 purse-string suture placed around the thoracostomy wound at the time of chest tube insertion and which will be used for the thoracostomy wound closure at the time of chest tube removal and Group B, that will not have a purse-string suture placement during chest tube insertion and will have their wounds covered by an occlusive adhesive-absorbent dressing material (Primapore\*), at the time of chest tube removal care and outpatient follow-up; will be similar for both groups and will follow a pre-determined standardized protocol. Specific clinical outcomes while the chest tube is indwelling and specific clinical and wound outcomes after the chest tube removal will be observed in both Groups for comparison and to determine causal relationships. Observations will be recorded in a specially-designed study proforma.

Principal Exposure: For Group A- Purse-string suture (U-suture technique) placement during

	chest tube insertion and purse-string suture closure of thoracostomy
	wound during chest tube removal
	For Group B- Non-placement of purse-string suture during chest tube
	insertion and use of occlusive adhesive-absorbent dressing during chest
	tube removal, for closure of the thoracostomy wound
Outcome variables:	- Clinical and wound complications with indwelling chest tube

- Early and late wound complications after chest tube removal

**Conclusion:** Data obtained from the prospective trial will provide general guideline for managing chest tube/thoracostomy wounds after chest tube removal. It will also be employed in the design of institutional protocol for chest tube insertion.

Keywords: Chest tube insertion, Purse-string suture, occlusive adhesive-absorbent dressing,

thoracostomy wound closure, wound complications

### CHAPTER ONE

#### INTRODUCTION/BACKGROUND

Closed thoracostomy tube drain insertion also referred to as tube thoracostomy, intercostal drainage or simply chest tube insertion is the most commonly performed surgical procedure in thoracic surgery (1). It is often performed routinely as part of the treatment of many thoracic diseases (2). This procedure largely involves placing a hollow and flexible drainage tube into the pleural space to remove an abnormal collection of air or fluid so as to permit re-expansion of the lung (3,4). It can also be used to infuse agents into the pleural space.

The wide use of chest drains became popular during the 1918 flu pandemic but they were first documented for the treatment of empyema by Hippocrates (5). Around the fourth century B.C, while using rudimentary skills of incision and cautery, he described the process of incising the chest and inserting a metal tube for pleural drainage (5,6).

Generally, the indications for inserting a closed thoracostomy tube drain include-pneumothorax, malignant pleural effusion, empyaema and complicated parapneumonic pleural effusion, traumatic haemopneumothorax; postoperatively after thoracotomy, pulmonary lobectomy, oesophagectomy, cardiac surgery; treatment with sclerosing agents or pleurodesis and post-pneumonectomy bronchopleural fistula (4,5,7,8,9). Table 1 below clearly summarizes these indications. The procedure is relatively contraindicated in patients with lung adherence to the chest wall and uncorrected coagulopathy (4).

The chest tubes inserted can be classified based on size or calibre into small-bore chest tubes and large bore chest tubes (9). The small-bore chest tubes (<20Fr) are indicated for spontaneous pneumothorax, free flowing pleural effusions or empyema while the large-bore chest tubes (>20Fr) are indicated for hemothorax, acute trauma, open thoracostomy, after most cardiothoracic, oesophageal or spine surgery (10).

The insertion of a chest tube and the ongoing care of patients with indwelling chest tubes carries the potential for significant morbidity and mortality if not properly done (10). Also, the safe closure of a chest tube insertion wound has been of great interest to surgeons for many years (11). Since chest tube insertion is considered a mandatory skill for different physicians including general and thoracic surgeons, interventional pulmonologists, intensivists and emergency medical specialists worldwide, there is an ever pressing need to develop a standard algorithm for removal of chest tubes (12).

#### **PROBLEM STATEMENT**

In spite of the ubiquitous placement of chest drains for different purposes, there is still a lack of highquality prospectively-designed evidence-based guideline for post-placement management of the chest tubes making current management of patients with chest tubes to be largely reliant on protocols of individual institutions and personal idiosyncrasies mostly borne out of anecdotal experience (13, 14) Several national and international thoracic societies' guidelines exist as well as published literatures that give clear advice on when to consider inserting chest drains (5,7,9). Also, there is a litany of procedural guidelines detailing how to safely perform chest tube insertion. However, there is a paucity of major guidelines or scientifically-proven standard methodology of closing the wound made during the process of chest tube insertion at the time of removal of the chest tube (9,11,15). The conventional method of managing a thoracostomy wound at the time of chest tube insertion is to use an anchoring suture to fix the chest tube to the wound edge thereby preventing it from spontaneously extruding while also placing a purse-string suture around the wound that would be used to close the wound at the time of chest tube removal (2,11). This purse-string suture can also be used as an additional means of securing the chest tube in position with the added advantage of preventing air or pleural fluid from entering or egressing the pleural space (i.e. air and water tightness) during the tube removal process (2). It has been reported that though beneficial for the most parts, this purse-string suture placement at the time of tube insertion has its inherent burden of suture-related pain, irritation and increased rates of wound infection following its placement and retention, an experience reported by patients during the course of the tube drainage and which may persist even after tube removal (11). It means this conventional method can be associated with higher drain removal pain scores and in addition, more frequent outpatient wound dressings after hospital discharge, need for suture removal after the wound has healed and the long-term development of an unsightly thoracostomy scar (2, 11,16). Skin staplers and simple interrupted skin sutures have also been used with equally unsatisfactory wound outcomes (2).

It has been noted that when petroleum gauze or any other adhesive and impermeant dressing material was used for air and water tight occlusion of the thoracostomy wound after chest tube removal (implying nonuse of a purse-string or any other type of suture), the incidence of iatrogenic pneumothorax and wound dehiscence was higher (2). Other more sophisticated suture techniques such as the use of knotless sutures, using a two-layer method with triclosan-coated sutures; appear to be more expensive to perform and require experience and uncommon expertise (15).

From the foregoing, it is clear that both the conventional suturing method as well as the alternative use of impermeant occlusive dressing of the thoracostomy wound after chest tube removal have their attendant problems. Studies that directly and deliberately compare outcomes and benefits of these two prominent thoracostomy wound management approaches are non-existent in medical literature.

#### **RATIONALE FOR THE STUDY**

The lack of evidence to support choice of thoracostomy wound closure at the time of removal of chest tube underscores the need for this study. There is no shortage of publications establishing an association between chest tube insertion as an invasive procedure and the occurrence of specific intervention-related early and late complications with variable degrees of impact on immediate and long-term outcomes of the disease indicating the tube insertion in the first place (4,6,7,9,11-16). Nonetheless, there are a few studies suggesting different techniques of closing a thoracostomy wound at the time of tube removal especially for those inserted following chest trauma as well as post-operation (thoracotomy and sternotomy) in which the tube is often inserted as an adjunct to a specific thoracic surgical procedure (15,16). It limits the generalizability of the findings of such studies knowing other non-traumatic thoracostomy indications abound beyond accidental and intentional trauma of surgery. Also, the review of all other similar studies indicates no universal or consensus decision on the most acceptable thoracostomy wound closure technique with a rarity of discussions about outcome of all suggested techniques especially as it relates to wound failure and cosmesis.

It is instructive to note that, this lack of evidence has contributed to why there is no recognized standardized or consensus method adopted by any of the globally renowned thoracic societies in their clinical practice guidelines as regards the technique of closure of the thoracostomy wound at the time of tube removal and till date controversies still exists about the most superior method amongst the few

described methods. Infact, no single prospective study has been done till date to establish the safest and best closure method that guarantees the best immediate and long-term wound outcomes after chest tube removal. This study is therefore required to answer these pending questions in a prospective manner within a real-life clinical practice setting.

# **OBJECTIVES OF THE STUDY**

### GENERAL OBJECTIVES

To prospectively compare the early and long-term outcomes between the use of purse-string (suturing U-technique) and Un-reapproximated thoracostomy wound edges (Occlusive adhesive-absorbent dressing application) at the time of removal of thoracostomy tube drain in patients who have had chest tube insertion.

### SPECIFIC OBJECTIVES

- To compare the tube-related complications of chest tube insertion in patients who have pursestring suture (U-suture placement) at the time of chest tube insertion versus those without pursestring suture placement that are enrolled for Occlusive adhesive-absorbent dressing application at the time of chest tube removal.
- To compare the incidence of early complications after chest tube removal in patients who have purse-string suture re-approximation of thoracostomy wound versus those who have only Occlusive adhesive-absorbent dressing application (Un-reapproximated wound edges)
- To compare the incidence of late wound complication after chest tube removal in patients who have purse-string suture re-approximation of thoracostomy wound versus those who have only Occlusive adhesive-absorbent dressing application (Un-reapproximated wound edges)

# **STUDY HYPOTHESIS**

NULL HYPOTHESIS: There is no difference in the wound and clinical outcomes of patients who had purse-string (suturing with U- technique) for closure and those who had an occlusive adhesiveabsorbent dressing application (Un-reapproximated wound edges); for post-tube removal management of thoracostomy wound

ALTERNATE HYPOTHESIS: There is a major difference in the wound and clinical outcomes of patients who had purse-string (suturing with U- technique) for wound closure and those who had an occlusive adhesive-absorbent dressing (Un-reapproximated wound edges); for post-tube removal management of thoracostomy wound

# STUDY VARIABLES AND DEFINITION

The independent variables to be employed for the analysis include:

- Age of the patient
- Sex of the patient
- Presence of specific co-morbidities (Diabetes, Hypertension, Chronic Liver disease, Chronic kidney disease)
- Charleson Comorbidity Index
- History of cigarette smoking and estimated pack years if positive

- Use of steroids and chemotherapeutic agent
- Abnormal Body mass index (Obesity(BMI> 30kg/m^2), Malnutrition(BMI< 18kg/m^2)

The Dependent variables to be employed for the analysis include:

- Presence of severe pain at the chest tube site after chest tube insertion (Average daily pain score after tube insertion > 5 on the Visual Analog Scale and or Numerical Rating Scale)
- Occurrence of tube dislodgement after chest tube insertion
- Occurrence of peri-tubal leakage of fluid after chest tube insertion
- Presence of wound air suck-in after chest tube removal (indicated by presence of air suck-in sound through the wound into the pleural space during quiet and or forced inspiration)
- Occurrence of wound infection after chest tube removal (presence of purulent or offensive wound discharge with or without fever or presence of wound discharge that is microbiologically positive)
- Occurrence of wound dehiscence after chest tube removal
- Occurrence of early (within 7 days) and late pneumothorax (more than 1 week) after chest tube removal confirmed on chest radiography
- Development of raised or elevated thoracostomy wound scars (unsightly scars appearing like hypertrophic scars or keloids) within 3 months of chest tube removal

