# **RESEARCH QUESTIONS**

- What is the difference in the tube-related complication rates after placing a purse-string suture (U suture placement and retention) for thoracostomy wound re-approximation versus non-placement of purse-string at the time of chest tube insertion?
- What is the difference in the early and late complication rates after using a purse-string suture (U suture) for thoracostomy wound re-approximation versus use of only an occlusive adhesiveabsorbent dressing with unreapproximated thoracostomy wound edges; at the time of chest tube removal?
- What is the difference in pain score after using a purse-string suture (U suture) for thoracostomy wound re-approximation versus use of only an occlusive adhesive-absorbent dressing with unreapproximated thoracostomy wound edges; after chest tube removal?
- Is purse-string thoracostomy wound closure associated with more cosmetic complications of thoracostomy scar in the long term than un-reapproximated thoracostomy edges with an occlusive adhesive-absorbent dressing ?

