# 3) Management of indwelling chest tubes

A chest radiograph will be done immediately after to ascertain the position of the tube and the degree of lung re-expansion. The drainage of the effluent is measured daily and charted; analgesia (combination of 1g oral paracetamol administered every 6hours at 6am, 12 noon, 6pm and 12 midnight; 50mg oral diclofenac sodium administered every 12hours at 10am and 10pm; and 50mg oral tramadol or 5mg oral morphine administered every 6hours at 9am, 3pm, 9pm and 3am) will be instituted for all patients in compliance with current unit analgesic protocol. All patients requiring therapeutic antibiotics (commenced empirically or with culture sensitivity guidance) will have the antibiotics administered according to the posology of the index medication. This category includes post-operative patients who have had chest tube inserted as an adjunct to surgery and those with any other indication for therapeutic antibiotics. All patients will have incentive spirometry (done with the standard threeball incentive spirometer, once every hour) and passive physiotherapy (three times a day). Daily dressing of the chest tube site will be done by the unit doctors during the daily ward rounds using 10% povidone iodine as described above. The pain intensity (pain scores) of the patients will be assessed at regular intervals (atleast twice a day; during morning and evening ward rounds) using the visual analogue scale (VAS), numeric rating scale (NRS) and Categorical verbal rating scale (VRS). Even though the VAS and the NRS have been shown to be superior to the VRS in the assessment of acute post-operative pain, all three will be employed in this study to enhance accuracy of assessment and minimize effect of subjectivity on observed pain scores as depicted in Figure 2 below (45).

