assistance. To ensure synchrony, a short count of one to three is done by the lead surgeon and by the count of three, he completes the knotting down to close the wound just as the tube is rapidly pulled out at a single swipe by the assistance upon completion of the count of three. There will be regular rehearsals and practice of these synchronous actions by all those who will be involved with this study as surgeons and assistants. The wound must be closed to air and water tightness but without strangulating the edges. The suture is trimmed, and a sterile dressing applied as before. There will be strict observance of aseptic technique by all involved in this tube removal process. A chest radiograph is done immediately after to check for presence of iatrogenic pneumothorax. The wound dressing will be removed on the third day and subsequent wound care will be determined by the finding at wound review by the principal investigator on this third day. The protocol to follow will be to continue daily povidone iodine wound care if there is evidence of wound infection but to leave the wound open to fresh air and apply povidone iodine topical cream till the suture is removed by day 7, after tube removal. The pain score will be assessed on a continuous basis (everyday till patient is discharged home and at every contact in the outpatient clinic). The patients will be followed up once a month for atleast 3 consecutive months after chest tube removal. Their pain score, wound outcomes and serial chest radiographic check (immediately after tube removal, at one week after tube removal and at every follow up visit in the outpatient clinic), will be done.

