#### DATA ANALYSIS AND MANAGEMENT

The data will be entered into the computer and thorough data cleaning will be done to check for errors and omissions at the end of data collection. The data was analyzed using Statistical Package for Social Sciences (SPSS) version 21. Descriptive statistics for baseline data shall be analyzed using mean, standard deviation, range and median, where appropriate, for any continuous variable and as percentages for any categorical variable. Baseline characteristics of the two study arms will be compared using Chi-square tests (for categorical variables) and student's t-test or analysis of variance (for continuous variables). Risk of complication will be evaluated using Cox-proportional analysis adjusting for potential confounders. Level of significance will be set at 5%. Findings will be presented in forms of texts, tables, figures and graphs as appropriate.

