(33) USE OF THERAPEUTIC A	ANTIBIOTICS YES() NO()	
IF YES, INDICATE THE GENE	ERIC TYPE , DOSE, FREQUENCY	AND DURATION IN DAYS
	R CHEST TUBE INSERTION):	,
PNEUMOTHORAX:	YES()	NO ( )
TUBE DISLOGDEMEN		NO ( )

SERIAL NO: .....

EMPYEMA:	YES ( )	NO ( )
WOUND INFECTION:	YES ( )	NO ( )
WOUND DEHISCENCE:	YES ( )	NO ( )
FLUID LEAKAGE:	YES ( )	NO ( )
AIR LEAK:	YES ( )	NO ( )
PAIN:	YES ( )	NO ( )

PAIN SCORE: DAY 1	6AM ( )	6PM( )
DAY 2	6AM ( )	6PM( )
DAY 3	6AM ( )	6PM( )
DAY 4	6AM ( )	6PM( )
DAY 5	6AM ( )	6PM( )
DAY 6	6AM ( )	6PM( )
DAY 7	6AM ( )	6PM( )
DAY 8	6AM ( )	6PM( )
DAY 9	6AM ( )	6PM( )
DAY 10	6AM ( )	6PM( )

# SERIAL NO: .....

(35) COMPLICATIONS (IMMEDIATELY AFTER CHEST TUBE REMOVAL):

PNEUMOTHORAX ON IMMEDIATE POST-TUBE REMOVAL CHEST XRAY: YES ( ) NO ( )

PNEUMOTHORAX ON CHEST XRAY DONE AFTER 1 WEEK:

	YES ( )	NO ( )
EMPYEMA:	YES ( )	NO ( )
WOUND INFECTION:	YES ( )	NO ( )
WOUND DEHISCENCE:	YES ( )	NO ( )
FLUID LEAKAGE:	YES ( )	NO ( )
AIR SUCK-IN THROUGH WOUN	ID:	
	YES ( )	NO ( )
MAJOR PAIN:	YES ( )	NO ( )
PAIN SCORE:		
DAY 1	6AM ( )	6PM()
DAY 2	6AM ( )	6PM()
DAY 3	6AM ( )	6PM()
DAY 4	6AM ( )	6PM()
DAY 5	6AM ( )	6PM()
DAY 6	6AM ( )	6PM()
DAY 7	6AM ( )	6PM()
DAY 8	6AM ( )	6PM()
DAY 9	6AM ( )	6PM()
DAY 10	6AM ( )	6PM( )

### (36) COMPLICATIONS AT FOLLOW-UP 1

PNEUMOTHORAX ON FOLLOW UP CHEST XRAY:

	YES ( )	NO ( )
WOUND INFECTION:	YES ( )	NO ( )
WOUND DEHISCENCE:	YES ( )	NO ( )

SERIAL NO:		
HYPERTROPHIC SCAR:	YES ( )	NO ( )
KELLOID:	YES ( )	NO ( )
WOUND PAIN:	YES ( )	NO ( )
IF YES, PAIN SCORE:		

# COMPLICATIONS AT FOLLOW-UP 2

WOUND INFECTION:	YES ( )	NO ( )
WOUND DEHISCENCE:	YES ( )	NO ( )
HYPERTROPHIC SCAR:	YES ( )	NO ( )
KELLOID:	YES ( )	NO ( )
WOUND PAIN:	YES ( )	NO ( )
IF YES, PAIN SCORE:		
PAIN SCORE:	6AM ( )	6PM ( )

# COMPLICATIONS AT FOLLOW-UP 3

WOUND INFECTION:	YES ( )	NO ( )
WOUND DEHISCENCE:	YES ( )	NO ( )
HYPERTROPHIC SCAR:	YES ( )	NO ( )
KELLOID:	YES ( )	NO ( )
WOUND PAIN:	YES ( )	NO ( )
IF YES, PAIN SCORE:		
PAIN SCORE:	6AM ( )	6PM ( )

# COMPLICATIONS AT FOLLOW-UP 4

WOUND INFECTION:	YES ( )	NO ( )
WOUND DEHISCENCE:	YES ( )	NO ( )
HYPERTROPHIC SCAR:	YES ( )	NO ( )
KELLOID:	YES ( )	NO ( )

SERIAL NO:		
WOUND PAIN:	YES ( )	NO ( )
IF YES, PAIN SCORE:	·	
PAIN SCORE:	6AM ( )	6PM ( )
COMPLICATIONS AT FOLLO	W-UP 5	
WOUND INFECTION:	YES ( )	NO ( )
WOUND DEHISCENCE	E: YES()	NO ( )
HYPERTROPHIC SCAF	R: YES ( )	NO ( )
KELLOID:	YES ( )	NO ( )
WOUND PAIN:	YES ( )	NO ( )
IF YES, PAIN SCORE	:	
PAIN SCORE:	6AM ( )	6PM ( )

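### The only listed pain outcome is a yes/no cut at a score above 5 after insertion, and the research question on pain score after removal has no outcome or analysis

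*Combined protocol and SAP*

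**What the plan says.** The dependent variables in Study Variables and Definition include one pain entry, the presence of severe pain at the tube site, defined as "Average daily pain score after tube insertion > 5 on the Visual Analog Scale and or Numerical Rating Scale". It is binary and covers only the period after insertion.

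The data collected are richer than that.
- **While the tube is in.** Management of Indwelling Chest Tubes states that "The pain intensity (pain scores) of the patients will be assessed at regular intervals", namely "atleast twice a day; during morning and evening ward rounds", on a visual analogue, a numeric and a verbal scale.
- **After removal.** Procedure for Chest Tube Removal, in the Group A text, says "The pain score will be assessed on a continuous basis", meaning daily until discharge and then at each clinic contact. The follow-up section has pain assessed in both groups.
- **On the form.** The Study Proforma has a grid starting "PAIN SCORE: DAY 1", with morning and evening boxes for ten days after insertion, and a second such grid after removal. The second grid stands beside an undefined yes/no item for major pain.

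The Research Questions ask, for the period after removal, "What is the difference in pain score after using a purse-string suture" rather than the dressing alone.

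Data Analysis and Management names Student's "t-test or analysis of variance (for continuous variables") for comparing baseline characteristics. For outcomes it says only: "Risk of complication will be evaluated using Cox-proportional analysis adjusting for potential confounders".

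**The concern.** The Problem Statement names suture-related pain, during drainage and possibly persisting after removal, as an inherent burden of the purse-string. Pain is therefore one of the reasons for testing the alternative. It is also the one listed outcome that is measured on a graded scale, repeatedly, in every patient. The other listed outcomes are events.

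The plan reduces this measurement to whether an average exceeds 5. A patient whose score would be 5 under one method and 2 under the other counts the same under both, and so does a patient at 9 or 6. For the period after removal the gap is of another kind. The plan asks a question about a score but defines no variable for it and names no test.

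Two things are at stake: power on an outcome that matters to the comparison, and freedom after the fact to choose among three scales and up to 20 readings per period.

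**Working it through.** **Plan's own figure.** There is none to reproduce for pain. The sample size rests on pneumothorax. The documents give no pain mean, SD, target difference or expected rate of severe pain, and no reason for the cut at 5.

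**Inputs from the documents.** 71 patients per arm, 5% non-response and a two-sided 5% level (Sample Size). Evaluable per arm: 71 × 0.95 = 67.45, taken as 67.

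**Assumed inputs.** Roughly normal patient-level scores, SD 2, a true difference of 1 point, and group means of 4 v 3 or 3 v 2.

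**Step 1: information kept by the cut.** For normal scores and a small shift, the efficiency of the yes/no comparison relative to the comparison of means is φ(c)² / [p(1 − p)]. Here p is the share of patients above 5, c is the matching normal quantile and φ is the normal density.

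| Share above 5 (assumed) | φ(c) | Efficiency | Loss |
|---|---|---|---|
| 50% | 0.399 | 0.159 / 0.25 = 0.64 | 36% |
| 30% | 0.348 | 0.121 / 0.21 = 0.58 | 42% |
| 20% | 0.280 | 0.0784 / 0.16 = 0.49 | 51% |
| 10% | 0.175 | 0.0308 / 0.09 = 0.34 | 66% |
| 5% | 0.103 | 0.0106 / 0.0475 = 0.22 | 78% |

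Under normality the loss is smallest, 36%, when half the patients exceed 5, and it grows as the share moves away from half.

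**Step 2: power for the mean.** The standardised difference is 1/2 = 0.5 and the noncentrality is 0.5 × √(67/2) = 2.89. A two-sided t-test has power of about 82%.

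**Step 3: power for the cut, same patients and same shift.** The proportion above 5 is 1 − Φ((5 − mean)/2).
- **Means 4 v 3.** The proportions are 30.9% and 15.9%, a difference of 0.150. The pooled standard error is 0.0731 and the unpooled 0.0719. Power = Φ((0.150 − 1.96 × 0.0731)/0.0719) = Φ(0.09) = 54%.
- **Means 3 v 2.** The proportions are 15.9% and 6.7%, a difference of 0.092. The standard errors are 0.0546 and 0.0541. Power = Φ((0.092 − 1.96 × 0.0546)/0.0541) = Φ(−0.28) = 39%.

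**Step 4: dependence on the normal shape.** Simulated scores bounded to 0–10, with a 1-point difference, gave the following power (mean v cut).

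| Assumed SD | Means 4 v 3 | Means 3 v 2 |
|---|---|---|
| 1.5 | 97% v 71% | 97% v 40% |
| 2 | 82% v 54% | 81% v 40% |
| 2.5 | 61% v 40% | 61% v 33% |

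The cut is weaker in every case.

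**Step 5: after removal.** No arithmetic applies. Set side by side, the Research Questions ask about a score, the list of dependent variables has no pain entry for that period, and the analysis section names no outcome method for a numeric variable.

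**The case against.** **The cut has a clinical meaning.** Follow Up and Treatment Adherence uses a score above 5 as the plan's own definition of poor pain control, and analgesia is escalated there. A yes/no outcome also fits the objective of comparing complications. This stands. It is a reason to keep the cut as a secondary outcome, not to make it the only one.

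**Escalation affects both versions.** Extra analgesia above 5 may narrow a difference in means as well as in proportions, so 82% should not be read as a forecast. This also stands, but it does not favour the cut.

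**The definition is ambiguous.** The average could be taken over the whole tube period, or the criterion could be met by any single day averaging above 5. The second reading gives a higher event rate, and the formula in Step 1 would not apply to it directly. This stands and belongs in the fix.

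**Stronger readings that the documents do not support.**
- A reader might infer that the plan is known to lose a third to two thirds of the information. That range needs roughly normal scores and 10% to 50% of patients above 5. The documents state neither, and below 10% the loss is larger.
- A reader might infer that data are thrown away. They are not. The scores stay on the proforma and the loss is in the planned outcome.
- A reader might infer that pain after removal is also cut at 5. The definition is limited to the period after insertion. The fault after removal is a missing outcome and analysis.

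**Conclusion.** The point holds in two parts. First, the only listed pain outcome is a binary cut on data collected numerically, and no outcome analysis of the scores is specified. Second, the research question on pain score after removal has no outcome variable and no test. Both follow from the text alone.

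The size of the first part is conditional. The 36% floor rests on rough normality, and the larger losses also rest on the assumed share above 5. The drop from 82% power to 54% or 39% rests on the assumed SD, difference and means. The direction does not depend on these values within the range examined. Every patient receives scheduled analgesia with several drugs, so scores above 5 may be a minority, which is where the cut costs most, but the plan gives no rate. Pain did not determine the sample size, so this is a worthwhile improvement and not a threat to the trial's stated basis.

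**What to change.** **Study Variables and Definition.** Name the patient's mean numeric score over a fixed, pre-stated window as the pain outcome, once for the period after insertion and once for the period after removal. State one governing scale, visual analogue or numeric rating, in place of the present either-or-both wording. Choose each window with the length of tube retention and the timing of discharge in mind, because daily scoring after removal stops at discharge.

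**Keep the cut as a secondary outcome.** Say whether above 5 refers to the average over the whole period or to any single day.

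**Data Analysis and Management.** For each period, compare the randomised groups by the difference in means with a 95% CI, or fit a mixed model to the repeated scores. Note that escalation of analgesia above 5 may narrow the difference in either version.

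**Cost.** A few sentences in two sections, fixed before the data are analysed, and a scale label on the proforma's pain boxes, which at present do not say which scale is recorded. No new data are needed.
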